10.4.2.2 Efficacy Analyses

Endpoint	Statistical Analysis Methods
Primary	
ORR per modified RECIST v1.1, ORR is defined as the incidence of a BOR of CR or PR
 
ORR: Binomial proportions and exact 95% CIs.

Secondary	
CRR is defined as the incidence of a BOR of CR.
 
DRR is defined as the percent of subjects with a CR or PR with a DOR \geq 6 months.
 
DCR is defined as the incidence of a BOR of CR, PR or SD.
 
DOR is defined as the time of an initial response (CR or PR) to PD or death, whichever is earlier. Subjects who have not ended their response at the time of analysis will be censored at their last evaluable tumor assessment before the start of the first subsequent anticancer therapy.
 
OS is defined as the time from enrollment to death. Subjects without an event will be censored at their last known to be alive date.
 
PFS is defined as the time from enrollment to PD or death, whichever is earlier. Subjects without an event will be censored at their last evaluable tumor assessment if available, otherwise will be censored on day 1.
 
Time to subsequent anticancer therapy is defined as the time from enrollment to the start of subsequent anticancer therapy. Subjects who have not started subsequent anticancer therapy will be censored on their last visit date.
 
iORR per modified irRC-RECIST, and CRR, BOR, DRR, and DCR, per modified RECIST v1.1 and modified irRC-RECIST will follow the analysis described for the primary endpoint: Binomial proportions and exact 95% CIs
 
DOR per modified RECIST v1.1 and modified irRC-RECIST: KM method among responders (CR and PR).
 
OS per modified RECIST v1.1 and modified irRC-RECIST: KM method.
 
PFS per modified RECIST v1.1 and modified irRC-RECIST: KM method.
 
Time to subsequent anticancer therapy: KM method.

Exploratory	
Will be described in the statistical analysis plan finalized before database lock

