10.4.2.3.6 Exposure to Concomitant Medication

Number and proportion of subjects receiving therapies of interest will be summarized by preferred term as coded by the World Health Organization Drug dictionary.

The subject incidence and time to first use of subsequent anticancer therapies will be summarized.

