PFS per modified RECIST 1.1 is defined as the interval from first dose to the earlier event of PD (per modified RECIST 1.1) or death from any cause. Subjects without an event will be censored at their last evaluable post-baseline tumor assessment if available, otherwise will be censored on study day 1.

- **Safety follow-up visit**

Safety follow-up visit will be performed approximately 30 (+7) days after the last dose of IP. If an end of treatment decision occurs > 30 (+7) days after the last treatment date, then safety follow-up will be performed as soon as possible (eg, within a week of end of treatment decision).

- **Serious adverse event (SAE)**

Serious adverse events (SAE) are defined as any adverse event categorized as serious as determined by investigator per protocol defined criteria.

- **Study day**

Study day is calculated from the first day IP is administered (i.e. non-zero dosing).

If visit date is on or after first dose date then:

$$\text{Study day} = \text{visit date} - \text{first dose date} + 1$$

if visit date is before first dose date then:

$$\text{Study day} = \text{visit date} - \text{first dose date}$$

- **Study week 0**

The start of IP administration (i.e. non-zero dosing) to the subject is study week 0. Study day 1 is corresponding to study week 0.

- **Time to subsequent anticancer therapy**

Time to subsequent anticancer therapy is defined as the time from enrollment to the start of subsequent anticancer therapy. Subjects who have not started subsequent anticancer therapy will be censored on their last visit date.

- **Treatment-emergent adverse events (TEAE)**

Treatment-emergent adverse events are defined as any adverse event occurring after initiation of the first dose of study therapy through 30 days after the last administration of study therapy. Adverse events that occur on the same day as the first dose date of study therapy will be treated as treatment-emergent events unless indicated otherwise (for example, if an event occurs on the same date as the first administration of study therapy and the check box indicating prior to the first dose of study therapy is checked on eCRF, then the event will not be counted as a treatment-emergent AE).

[figure not shown]
- **Treatment-emergent serious adverse events (TESAE)**

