9.1 General Considerations

Unless otherwise specified, all safety analysis will be performed on the SAS and all efficacy analysis on the FAS. All analyses will be descriptive with no formal hypothesis testing. Analyses will be performed separately for each cohort. In addition, analyses with cohorts pooled together (all cohorts pooled, cohorts 1 and 2 pooled, and cohorts 3 and 4 pooled) will be performed. Cohorts stopped for futility will not be pooled with other cohorts. Cohort data collected on the CRF will be used in the analysis. Cohort data will be checked and reviewed during the study to ensure that subjects are recorded in the correct cohort for analyses prior to database lock.

Continuous variables will be summarized by the non-missing sample size (n), mean, standard deviation, median, first and third quartiles, minimum, and maximum.

Categorical variables will be summarized by the n and percentage in each category.

Proportions and the corresponding 95% exact CIs will be provided ([Clopper and Pearson, 1934](#)).

[REDACTED], time to event endpoints will be summarized with Kaplan-Meier (KM) ([Kaplan and Meier, 1958](#)) curves, KM estimates at selected time points, KM quartiles (when estimable), the number of subjects with events and the number of subjects censored. Accompanying 2-sided 95% CI for KM quartiles ([Brookmeyer and Crowley, 1982](#)) and KM estimates will be provided.

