9.5.2 Analyses of Secondary Efficacy Endpoint(s)

CRR, BOR, DRR and DCR by investigator assessment using modified RECIST 1.1 and iORR, iCRR, iBOR, iDRR and iDCR by investigator assessment using modified irRC-RECIST will be summarized with associated exact 95% CIs for binomial proportions ([Clopper & Pearson 1934](#)) (see code fragment in [Appendix B](#)).

KM estimates and quartiles for DOR, iDOR, PFS, iPFS, OS and Time to subsequent anti-cancer therapy will be provided ([Kaplan and Meier, 1958](#)). KM time to event curves will be presented.

The impact of subsequent anti-cancer therapy on PFS, iPFS and OS will be assessed by censoring at the last evaluable tumor assessment prior to the start of the first subsequent anti-cancer therapy.

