9.6.8 Exposure to Concomitant Medication

The number and proportion of subjects receiving therapies of interest will be summarized by preferred term or category for each cohort as coded by the World Health Organization Drug (WHO DRUG) dictionary.

The number and proportion of subjects receiving subsequent anti-cancer therapies will be summarized by preferred term or category for each cohort as coded by the World Health Organization Drug (WHO DRUG) dictionary.

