9.7 Other Analyses

ECOG performance status scores will be summarized at each time point. Changes in scores for ECOG performance status scores from baseline will also be tabulated.

Spider plots for subject-level percent change from baseline in tumor burden by BOR per modified RECIST 1.1 and iBOR per modified irRC-RECIST and disease stage at baseline will be provided. Waterfall plots for subject-level maximum overall tumor burden reduction by BOR per modified RECIST 1.1 and iBOR per modified irRC-RECIST will also be summarized. Tumor assessments occurring after the start of the first subsequent anti-cancer therapy will be excluded from the analysis of tumor burden. With the exception of tumor assessments with an increase of tumor burden $\geq 20\%$ and also demonstrate ≥ 5 mm increase from nadir, tumor assessments occurring on or after the complete or partial removal/reduction of any target lesion with melanoma on pathology evaluation or unknown pathology results will also be excluded from the analysis of tumor burden.

10. Changes From Protocol-specified Analyses

Not applicable.

11. Literature Citations / References

Brookmeyer R and Crowley J. A confidence interval for the median survival time. *Biometrics*. 1982;38:29-41.

Clopper, C. and Pearson, E. (1934) "The Use of Confidence or Fiducial Limits Illustrated in the Case of the Binomial," *Biometrika*, 26, 404–413

Eisenhauer, A., et al (2009) "New Response Evaluation in Solid Tumors: Revised RECIST Guideline (version 1.1)", *EJC*, 45, 228-247.

[figure not shown]
Lin, Guixian, Ying So, and Gordon Johnston. "Analyzing survival data with competing risks using SAS software." *SAS Global Forum*. Vol. 2102. 2012.

[figure not shown]
Pintilie, M. (2006) *Competing Risks: A Practical Perspective*. Wiley.

<http://dx.doi.org/10.1002/9780470870709>

12. Appendices

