Appendix A. Reference Values/Toxicity Grades

Appendix B. Technical Detail and Supplemental Information Regarding Statistical Procedures and Programs

B.1 Clopper-Pearson Exact Confidence Interval

```
proc freq data=data1;  
tables var1/ binomial(exact);  
run;
```

B.2 Non-parametric cumulative incidence function (CIF)

```
proc lifetest data=event_data outcif=cif plots=cif(test);  
time timevar*cnsr(1)/eventcode=0;  
ods output;  
run;
```

Variable cnsr:

Value 0 = █████ progression event
1 = censored
2 = competing risk event

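### Time to subsequent anticancer therapy censors untreated deaths but is summarised by Kaplan-Meier, so uptake is overstated and the median and upper quartile can be too early; cumulative incidence should be the main summary

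*SAP*

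**What the plan says.** SAP Section 5 defines time to subsequent anticancer therapy as running from enrollment to the start of such therapy. Its censoring rule is: "Subjects who have not started subsequent anticancer therapy will be censored on their last visit date". Death has no exception. In the same section death is an event for PFS, iPFS, DOR and iDOR.

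SAP 9.5.2 names the method: "KM estimates and quartiles for DOR, iDOR, PFS, iPFS, OS and Time to subsequent anti-cancer therapy will be provided". Protocol 10.4.2.2 agrees: "Time to subsequent anticancer therapy: KM method". Some words before the general Kaplan-Meier sentence in SAP 9.1 are redacted, but that leaves no doubt here, because 9.5.2 names this endpoint explicitly.

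Three other outputs accompany the curve:
- SAP 9.1 asks for "the number of subjects with events and the number of subjects censored".
- Protocol 10.4.2.3.6 states: "The subject incidence and time to first use of subsequent anticancer therapies will be summarized".
- SAP 9.6.8 states: "The number and proportion of subjects receiving subsequent anti-cancer therapies will be summarized by preferred term or category for each cohort".

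SAP Appendix B.2 contains cumulative-incidence code with a competing-event value, but its event of interest is a (partly redacted) progression event. No readable text applies it to this endpoint. SAP Section 10, "Changes From Protocol-specified Analyses", records none.

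A related sentence at the end of SAP 9.5.2 plans to assess the impact of subsequent therapy on PFS, iPFS and OS by censoring at the last evaluable tumor assessment before that therapy.

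**The concern.** Kaplan-Meier treats a censored subject as someone who could still have the event later, at the rate seen in those who remain at risk. That does not hold for a subject who has died. The curve then describes a world in which nobody dies before further treatment, whereas readers will take its median and quartiles as when, and how often, these patients went on to other therapy.

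Follow-up runs to 36 months after the last subject is enrolled (Protocol 9.1.4), in patients with advanced melanoma who have already progressed on anti-PD-1 therapy. Some untreated deaths are to be expected, and their effect accumulates between the primary analysis (at least 24 weeks of follow-up, SAP 7.2) and the final analysis (SAP 7.3). The study is purely descriptive, so the reported estimate is itself the result.

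**Working it through.** **Inputs.** The event, censoring rule and method are those of SAP Sections 5 and 9.5.2. The documents state no figure for this endpoint, so there is none to reproduce. They also give no hazard for therapy start or untreated death, so every rate below is an assumption.

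**Direction, by counting.** Take 72 subjects, 36 therapy starts, 12 untreated deaths, and no other censoring before the last start. The true proportion starting therapy is 36/72 = 50.0%.
- All 12 deaths before the first start: 60 remain at risk, and 1-KM ends at 36/60 = 60.0%.
- Deaths spread randomly among the starts: 1-KM averages 56.1%.
- All deaths after the last start: 1-KM = 36/72 = 50.0%, no bias.

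So 1-KM is never below the cumulative incidence, and exceeds it once an untreated death precedes a later start. With 4, 8 or 18 deaths spread among the starts it averages 51.8%, 53.8% or 60.3%.

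**Size, closed form.** Let *a* be the therapy hazard and *d* the hazard of death without therapy, both constant per month:

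- 1-KM(t) = 1 - exp(-a·t)
- CIF(t) = [a/(a+d)]·[1 - exp(-(a+d)·t)]
- share of first events that are untreated deaths: s = d/(a+d)
- KM time to reach proportion p: -ln(1-p)/a
- CIF time to reach p: -ln(1 - p(a+d)/a)/(a+d), if a/(a+d) > p; otherwise never reached

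Worked case, a = 0.08, d = 0.04, t = 24: 1-KM = 1 - exp(-1.92) = 85.3%; CIF = (2/3)·[1 - exp(-2.88)] = 62.9%; difference 22.4 points.

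Ranges over a = 0.04, 0.06, 0.08:

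| Quantity | s = 5% or 10% | d = 0.02, 0.03, 0.04 (s = 20-50%) |
|---|---|---|
| Overstatement at 24 weeks (5.52 months), points | 0.1-0.8 | 1.0-3.4 |
| At 12 months, points | 0.4-2.7 | 3.9-10.8 |
| At 24 months, points | 1.3-6.0 | 10.8-22.4 |
| KM median too early by, months | 0.2-0.9 | 1.1-12.4, or CIF median not reached |
| KM third quartile too early by, months | 1.2-5.7 | 10.4 at 0.08/0.02 (17.3 against 27.7); otherwise CIF third quartile not reached |

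Medians, KM against CIF: 8.7 against 9.8 months (0.08/0.02); 17.3 against 29.7 (0.04/0.03). At 0.04/0.04, KM reports 17.3 months although the cumulative incidence can never pass 0.04/0.08 = 50%. The lower quartile moves little at low death rates: 7.2 against 7.3 months at a = 0.04, s = 10%.

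**Censoring at the last visit rather than at death.** A simulation (N = 72, 12-month accrual, KM median 9 months, d/a = 0.25) gives a 24-month 1-KM of 84.3% with censoring at death and 85.0% with censoring at the last 12-weekly visit, against a true 72.0%. The last-visit rule adds slightly to the overstatement.

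**Against sampling error.** The exact 95% CI widths in SAP 3.2 are 47.3 points at N = 15 and 21.0 at N = 72. Sampling error dominates within a cohort, but the bias is systematic and does not shrink with pooling.

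**OS sensitivity sentence (minor).** OS does not depend on tumor assessments. Censoring it at one drops known survival time and later deaths, and the censoring is related to prognosis. An illness-death simulation with no therapy effect (assumed monthly hazards: progression 0.12, death 0.01 before and 0.05 after progression) has a true 24-month OS of 43%. With switching after progression unrelated to prognosis, the censored estimate is 43.4-45.3% at 20-40% switching and 44.4-60.5% at 60-100%. With a two-fold difference in post-progression death hazard it is 42.5-44.9% if fitter patients switch more and 44.8-48.9% if sicker ones do (true 43%). With a five-fold difference it is 35.3-44.8% or 47.2-58.4% (true 45%). At 24 weeks the shift is at most 1.1 points. It can go either way or be near zero.

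**The case against.** The strongest reply is that Kaplan-Meier validly estimates a hypothetical quantity (no deaths, independent censoring), and that neither document says 1-KM will be reported as uptake. That is true, but the SAP states no such hypothetical target, and an unlabelled median time to subsequent therapy will be read as a description of these patients.

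Second, the crude incidence in Protocol 10.4.2.3.6 and SAP 9.6.8 answers how often. By the final analysis, apart from withdrawal and loss, it should be close to the cumulative incidence at end of follow-up. This stands as partial mitigation. It does not correct the curve's quartiles or its estimates at particular times.

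Third, all hazards are assumed, and constant hazards from day 0 fit poorly with a first on-treatment scan at week 12. A model in which therapy follows scan-detected progression gives a 24-week gap of about 0.3-1.5 points, against 1.0-3.4 in the higher-death scenarios above. The figures are illustrations, then, and the early effect may be smaller; later gaps in that model remain material.

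Fourth, the direction is conditional: no bias arises if every untreated death follows the last therapy start. That also stands.

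Finally, the endpoint is descriptive with no special rank, and the key-secondary heading covers every secondary objective. This limits the importance of the point but does not make the summary right.

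**Conclusion.** The concern holds. The plan censors untreated deaths and summarises the endpoint by Kaplan-Meier. As a description of when subjects start further therapy, the curve is biased early once any untreated death precedes a later start, with the median and upper quartile affected most.

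The direction rests on no assumption beyond that ordering. The size rests entirely on assumed constant hazards: small at the primary analysis, and from about 1 to about 22 points at 24 months across the scenarios considered. The change should be made but is not critical. It touches one descriptive secondary endpoint and leaves ORR, sample size, futility and the main OS analysis alone. The OS sensitivity sentence is a separate, minor fault; the main OS definition is sound.

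**What to change.** - In SAP 9.5.2, make the cumulative incidence of subsequent therapy the main summary. Death without subsequent therapy is the competing event, dated at death; living subjects without therapy stay censored. The Appendix B.2 code form serves, with new event codes.
- Keep the protocol-specified Kaplan-Meier summary only if labelled as a hypothetical estimate in the absence of death.
- Record the change in SAP Section 10, since it departs from the method in Protocol 10.4.2.2. Do not redefine the endpoint.
- Delete OS from the sensitivity sentence at the end of SAP 9.5.2. Leave the PFS and iPFS sensitivity analyses as they are.

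The cost is SAP wording and programming; therapy and death dates are already collected. The reported median time to therapy will lengthen or may not be reached, and the supplementary OS curve will not be produced.

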6.1 Full Analysis Set

The Full Analysis Set (FAS) is defined as all enrolled subjects who have received at least 1 dose of talimogene laherparepvec and 1 dose of pembrolizumab in combination. The FAS will be used in the analysis of the efficacy endpoints.

6.2 Safety Analysis Set

The Safety Analysis Set (SAS), defined as all enrolled subjects who received at least 1 dose of talimogene laherparepvec or pembrolizumab, will be used in the analysis of the safety endpoints.

6.3 Per Protocol Set(s)

The Per Protocol Analysis Set (PPAS) is a subset of the FAS which includes subjects who do not have important protocol deviations that are considered to have an impact on efficacy outcomes.

Subjects with any of the following eligibility criteria for important protocol deviations will be removed from the PPAS:

- Subject does not have histologically confirmed diagnosis of melanoma
 - Subject does not have unresectable or metastatic melanoma, defined as either
 - Stage IIIB, IIIC, IIID, IVM1a, IVM1b, or IVM1c;
- OR
- Stage IVM1d with up to 3 cerebral metastases, provided that all lesions have been adequately treated with stereotactic radiation therapy, craniotomy, or gamma knife therapy, with no evidence of progression and not requiring steroids for at least 2 months prior to enrollment.
- Subject is not a candidate for intralesional therapy, and a candidate is defined as either one of the following:
 - At least one injectable cutaneous, subcutaneous, or nodal melanoma lesion equal to or greater than 10 mm in longest diameter;
- OR
- Multiple injectable melanoma lesions which in aggregate have a longest diameter of equal to or greater than 10 mm

Additionally, the subjects with any of the following important protocol deviations related to prior PD-1 inhibitor use will be removed from the PPAS:

- Subject has not received prior treatment with a PD-1 inhibitor in the adjuvant or metastatic setting (monotherapy or in combination with anti-CTLA-4). Combinations other than anti-PD-1 plus anti-CTLA-4 must have been reviewed with the medical monitor for approval.
- Subject has not received prior anti-PD-1 therapy for at least 2 to 3 consecutive cycles within an 8-week period (based on administration schedule).
- Subject for whom the anti-PD-1 therapy is not the immediate prior line of therapy before enrollment.

[figure not shown]
The PPAS will be used in the analysis of the select efficacy endpoints.

6.4 Study-specific Analysis Sets

6.4.1 qPCR Suspicious Lesion Swab Analysis Set

The qPCR Suspicious Lesion Swab Analysis Set will include subjects who are in the FAS, receive at least one dose of talimogene laherparepvec, and have at least one swab sample evaluable result from lesions suspicious to be herpetic in origin during the study.

Evaluable samples are sample with either positive, below quantification limit (BQL), or not detected results.

7. Planned Analyses

7.1 Interim Analysis and Early Stopping Guidelines

[figure not shown]
Futility analyses are not planned for cohorts 3 and 4. In cohorts 1 and 2, if there is at least 1 unconfirmed responder (PR/CR as per modified RECIST 1.1) in the first 10

subjects of a cohort, enrollment will continue in that cohort without a futility analysis. Otherwise, the DRT will oversee a futility analysis of unconfirmed response for cohorts 1 and 2, performed separately and only once for each cohort, when 15 subjects within a cohort are evaluable for response (i.e. when 15 subjects have been treated and have had the opportunity to be followed for at least 12 weeks for tumor assessment). Screening in the respective cohort will be paused during the futility analysis. The below table presents the futility criteria:

Number of Evaluable Subjects* at Futility Analysis	Minimum Number of Subjects with an unconfirmed CR/PR to Continue	Probability of Futility (%) True ORR = 25%
15	1	< 5%

* number of subjects treated and who have had the opportunity to be followed for at least 12 weeks for tumor assessment.

When the true response is 25%, the probability of futility is < 5% with at least 1 responder among 15 evaluable subjects.

A data review team (DRT) will review safety data approximately every 3 months until the data snapshot for the primary analysis to ensure no avoidable increased risk for harm to subjects. In addition, the DRT will oversee the futility analysis for each of cohorts 1 and 2. The DRT may request ad hoc meetings at any time. The DRT also has a responsibility to review and evaluate study conduct to determine whether the study integrity may affect the ability of the DRT to fulfill its primary responsibility. Therefore,

the DRT will review and evaluate eligibility/recruitment/retention of participants, management of participants, and adherence to protocol-specified criteria. The DRT will make recommendations concerning the continuation or alteration of the study on the basis of its review of the data.

The DRT will be comprised of an Amgen clinical research medical director, Amgen safety officer, and Amgen biostatistician who are external to the talimogene laherparepvec product team.

Membership, procedures, and meeting timing will be described in the study DRT charter.

